1.0 Objectives / Specific Aims

- Objective: Study the safety and efficacy of uniform nonequilibrium, nonthermal atmospheric pressure plasma (NTAP)/cold atmospheric plasma device (CAP) in the treatment of molluscum contagiosum and vercurra (warts) in children 4-21 years.
- Aim:
 - Measure the changes in size, pain and appearance of verrucae and molluscum after 4, 8 and 12 weeks.
 - Evaluate the safety profile and patient tolerability of the treatment by analyzing potential side effects and pain levels, or lack thereof, with each treatment.
- Hypothesis: NTAP will be an equally efficient and painless alternative to cryotherapy for the treatment of molluscum and warts.

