3.0 Intervention to be studied (if applicable)

We will utilize a floating electrode-dielectric barrier device (FE-DBD) Cold atmospheric plasma (CAP) device on molluscum and warts in children and adolescents 4-21 years (Figure 1). Children and adolescents are targeted because they are the population most affected by painful standard of care therapy. The study will continue until at least 68 warts and 68 molluscum are treated. Each patient will not have more lesions treated than SOC recommendations. Half the lesions will be treated with plasma and the other half with standard of care being cryotherapy for warts and cantharidin for molluscum. A single patient must have minimum of 1 clinically diagnosed lesion treated and maximum of 20 treated. Lesions with a clinical impression of warts or molluscum will be selected. Selection of treatment type (control vs NTAP) will be randomly selected. Lesions

Page 3 of 13

The treatment device in this study generates cold atmospheric plasma. Cold atmospheric plasma has certain properties of plasma, such as ionized gas molecules. To create plasma, a pulse generator supplying 20-kV pulse of 20-ns pulse width at 200 Hz (FPG10-01NM10, FID GmbH, Burbach, Germany) to a 5-mm diameter quartz-covered copper electrode of 10-cm length and 1-mm quartz thickness (5). These nanosecond pulse parameters were chosen to provide sufficient treatment dose at the high level of plasma uniformity required to avoid any tissue damage. We treated the lesions for approximately 1 to 2 minutes each, moving the electrode gently over the treatment area.

After the study treatments are completed, we will analyze the data to see if the treatment was safe and effective.

Non-significant risk device statement (6-19) (Figure 1)

- We are proposing a clinical trial floating electrode-dielectric barrier device (FE-DBD) a Cold Atmospheric Plasma (CAP) device.
- While novel to the medical field and especially to dermatology, there are already a number of publications regarding its use on human skin in adults (20-26) and children (29).
- CAP devices utilize noble gases (such as helium) to deliver plasma state matter to the skin. As
 its name implies, the generated plasma stream is of near skin temperature and it exists on
 normal atmospheric pressure. During the generation of the plasma there is no electric contact
 with the patient. The treatment does not increase skin surface temperature and the used helium

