1.0 Study Endpoints (if applicable)

- Clinical assessment response after 4, 8 or 12 weeks. This will be assessed by a blinded study team member comparing clinical photographs and dermascopic images.
 - Clinical photographs measured by no response, partial resolution, complete resolution.
 - Dermoscopy images: no response, partial resolution, complete resolution using the guidelines below that indicate the presence of wart or mollusum.
 - Molluscum: Visualization of a central umbilication with polylobular, white to yellow, amorphous structures is typical. A peripheral crown of radiating or punctiform vessels is also present.
 - Wart: grouped papillae, with dotted or loop vessels, and/or hemorrhagic points and lines often surrounded by a whitish halo
- Visual analogue scale for experimental treatment and control treatment
 - The visual analogue scale (VAS) is a validated subjective measurement of pain experienced by the patient. It consists of visual-numeric scale, numbered from 0-10. (0) indicate absence of pain or "no pain at all", while (10) indicates severe pain or "worst imaginable pain". This is supplemented by six faces with different expressions, ranging from happy to extremely upset. Each facial expression is assigned a numerical scale from 0 to 10.
- Evaluation of tolerability included assessment of dry ness, peeling, scaling, erythema, edema, stinging, burning sensation, itching, scaring and dyspigmentation. They will be assessed by means of a standardized grading scale (0 = absent; 1 = mild; 2 = moderate; 3 = severe)

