6.0 Number of Subjects

Total of 150 would be required (half control, half NTP) to achieve 80% power with an alpha of

.05.

Calculation:

- Assumption for Probabilities for the Null hypotheses is P1=P2=P3=1, hence P1 = .333333, P2 = .333333, P3 = .333333 and P1+P2+P3 = 1.0 or that each proportion has an equal chance.
- Assumption for Probabilities for Alternative Hypothesis is taken from Provided NTP paper where P1=9/17 (Full Resolution = .53), P2=3/17=.18 (Some Improvement), and P3=5/17=.29 (no improvement).

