- Patient will return to the office for a 4-week standard of care follow-up. Study cessation or additional treatment will be determined by the provider assessment of lesion clearance. If lesion persist another treatment will occur. No greater than 3 treatments will be performed.
- This study will be single blinded, meaning the study team member accessing the results will
 not know which lesions were treated with what therapy. Assessment of clearance will be based
 off of clinical examination and images. The team will record any additional clinical feature
 that may arise during the analyses.

11. Data Management

- Continuous data will be summarized using descriptive statistics (number of values, means, standard deviation, median, minimum and maximum). Categorical data will be summarized using frequency tables (frequencies and percent).
- Chi-square analysis comparing the proportions of successes (equal chance outcomes).
- Coded dermoscopic and clinical photographs may be obtained for further analyses after each visit. Files with patient images will be stored in a secure departmental drive that will only be accessible to study team members by their unique MUSC ID and password.
- All subject medical record information and data collection will be coded and stored on an MUSC Box drive only accessible to study team members and will be protected by two-factor authentication. The linking document between ID and PHI will be maintained separately from the study data in a separate encrypted folder.

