15.0 Risks to Subjects

Risk for NTAP: To date, there are no known side effects or risks associated with the use of cold atmospheric or studies producing discomfort or pain (20-26, 29). However, because this is an experimental device, side effects like blistering, scarring, significant pigmentary alteration, and/or persistent nail change could occur and will be monitored at each visit, as well as pain assessment at every treatment session by validate pain scale (VAS).

The treatment received may prove to be less effective or to have more side effects than the other study treatment(s) or other available treatments.

This is a new device and even though no side effects of this treatment are reported in literature to date (27), the IRB will be notified via amendment, as well as participants via phone call if one arises.

There is a risk for possible breach of confidentiality. However, all measures to keep information protected will be taken. Photographs will be stored in the coded study-specific medical record for further analysis of lesion features. Only study team members will be able to access.

A cumulative data assessment will be conducted every other month throughout the study's duration by study team members. A report that includes any available efficacy data, as well as a record of anticipated adverse events, can be compiled and submitted to the IRB at that time. Any event meeting the criteria of an unanticipated problem involving risks to subjects or others will be immediately reported to the MUSC IRB, as required by HRPP 4.7- Unanticipated Problems and Adverse Events Policy and Procedures.

The plan for subject safety and minimizing risks of the research is assessing AE during, immediately following treatment and a few days after. Participants are encouraged to reach out to the study team if they think they are experiencing any adverse events. Other expected adverse effects deemed intolerable by the patient will prompt reduction in the patient's frequency, duration and treatment if indicated. Any condition necessitating cessation of the study drug will be followed to resolution.

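### The hypothesis claims equal efficacy, but the only planned test is a chi-square with no margin or confidence-interval criterion, so no result of it could support the claim

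*Combined protocol and SAP*

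**What the plan says.** The hypothesis in section 1.0 (Objectives / Specific Aims) is that "NTAP will be an equally efficient and painless alternative to cryotherapy for the treatment of molluscum and warts".

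The inferential plan is a single bullet under section 11, Data Management: "Chi-square analysis comparing the proportions of successes (equal chance outcomes". The other analysis text there is descriptive: summary statistics and frequency tables.

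Section 6.0 (Number of Subjects) gives the size: "Total of 150 would be required (half control, half NTP) to achieve 80% power with an alpha of" .05. Its null is "Assumption for Probabilities for the Null hypotheses is P1=P2=P3=1, hence P1 = .333333, P2 = .333333, P3 = .333333". Its alternative (9/17, 3/17 and 5/17 for full, some and no improvement) comes from an earlier NTAP paper. It gives no response rate for standard of care.

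Section 3.0 gives a lesion target, with half the lesions to go to each treatment: "The study will continue until at least 68 warts and 68 molluscum are treated".

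The Study Endpoints section defines response in three levels ("Clinical photographs measured by no response, partial resolution, complete resolution"), repeats them for dermoscopy, and gives the timing as "Clinical assessment response after 4, 8 or 12 weeks". It does not say which level counts as a success.

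No section states an equivalence or non-inferiority margin, a confidence-interval criterion, or a rule for concluding that the treatments are equally effective.

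**The concern.** A claim that a new treatment works as well as an active comparator needs a criterion that the data can meet, normally a confidence interval for the difference lying inside a margin chosen in advance. A chi-square test looks for a difference. It can give evidence against equality, but failing to find a difference is not evidence for equality, least of all in a small trial.

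At stake is the trial's main efficacy conclusion. If the result is not significant, the plan offers nothing that separates two treatments that perform alike from a trial too imprecise to tell. A reader who starts from the section 1.0 hypothesis could easily take the second for the first.

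**Working it through.** **1. The plan's own figure.** Section 6.0 states a total of 150 for 80% power at alpha 0.05. Its two probability sets, (9/17, 3/17, 5/17) and (1/3, 1/3, 1/3), were put into a noncentral chi-square calculation with 2 degrees of freedom.
- One-sample goodness of fit: w² = Σ(p1 − p0)²/p0 = 0.194, which needs N = 50. Power at 150 is 99.9%.
- Two-arm 2×3 table with these sets as the arms: w² = 0.0476, which needs N = 203 in total. Power at 150 is about 67%.

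Neither gives 150, so the figure does not show which test was meant. That is a separate matter, and the present point does not depend on it.

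**2. The two readings of the chi-square.**

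| Reading | Support in the text | Significant result | Non-significant result |
|---|---|---|---|
| Two-arm comparison | Section 11 speaks of comparing proportions; section 6.0 splits the total between control and NTAP | Contradicts equality | Does not establish equality |
| Goodness of fit to 1/3 each | The null in section 6.0; the bracketed words in the section 11 bullet echo it | Outcome categories are not equally likely | No evidence that they are unequal |

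On the first reading no result supports the hypothesis. On the second, standard of care is not in the test, so no result bears on a comparison with it.

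**3. Illustration, two-arm reading only.** From section 3.0, at least 68 lesions per disease split in half gives n = 34 per arm, which is a floor. Assumptions: independent lesions, and standard-of-care complete resolution p from 0.40 to 0.80, because the documents give no rate.

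*95% CI half-width if both arms share rate p:* 1.96 × √(2p(1 − p)/n).
- p = 0.40: 1.96 × 0.1188 = 0.233
- p = 0.50: 1.96 × 0.1213 = 0.238
- p = 0.80: 1.96 × 0.0970 = 0.190

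That is about 19 to 24 points.

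*Chance that a true 15-point NTAP deficit is non-significant* (two-sided 5%, pooled-variance test): power ≈ Φ((0.15 − 1.96 × SE0)/SE1). SE0 uses the mean of the two rates and SE1 the separate rates.
- Standard of care 0.80, NTAP 0.65: SE0 = 0.1083, SE1 = 0.1068, non-significant 0.720
- Standard of care 0.575, NTAP 0.425: SE0 = 0.1213, SE1 = 0.1199, non-significant 0.767 (the largest value in the range)
- Standard of care 0.40, NTAP 0.25: SE0 = 0.1136, SE1 = 0.1121, non-significant 0.741

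That is about 72% to 77%. Exact binomial enumeration of the same test gives 0.705 to 0.780.

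*Smallest margin that could be met with 80% power if the treatments are truly equal:*
- Non-inferiority, (1.960 + 0.842) × √(2p(1 − p)/n): 2.802 × 0.0970 = 0.272 to 2.802 × 0.1213 = 0.340, about 27 to 34 points
- Equivalence, both limits inside the margin, (1.960 + 1.282) × √(2p(1 − p)/n): 3.242 × 0.0970 = 0.314 to 3.242 × 0.1213 = 0.393, about 31 to 39 points

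**4. Pairing.** Section 10.0 divides multiple lesions equally between treatments within a participant. If all lesions formed 1:1 pairs with correlation r, the half-width would be multiplied by √(1 − r). At an assumed r = 0.5 it is 0.134 (p = 0.80) to 0.168 (p = 0.50). Over r from 0 to 0.5 the range is therefore 13 to 24 points. Single-lesion participants gain nothing from pairing, and a treatment effect that varies between participants would widen the interval.

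**The case against.** The strongest defence is that the study is exploratory. Its objective is to study safety and efficacy, its aims are to measure change and evaluate tolerability, and nowhere does it say that a non-significant result will be read as equality. All of that is true. A reader might infer that the plan intends to claim equality from a non-significant chi-square, but the documents do not support that; the defect is that no criterion is stated. Section 6.0 nevertheless claims 80% power at a set alpha, so the plan does present a formal test, and that test does not address the stated hypothesis.

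A reader might also infer that the hypothesis could be neither supported nor refuted. The second half does not hold on the two-arm reading, because a significant result favouring standard of care would contradict equality. With 75 per arm (section 6.0's total of 150 halved, diseases pooled, unit not stated) and the same assumptions, a true 20-point deficit would be detected about 69% to 77% of the time.

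It can also be said that the figures rest mainly on assumed rates and deficits, and that they fall away if the test is goodness of fit. Both statements are correct. The figures show scale on one reading, and the conclusion does not depend on them.

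**Conclusion.** The point holds and should be fixed. Under either reading of the chi-square, no result of the stated analysis could support the efficacy part of the section 1.0 hypothesis. This follows from the text alone.

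The size of the problem is conditional. It applies only to the two-arm reading, at the minimum lesion count for one disease, with independent lesions and an assumed standard-of-care rate of 0.40 to 0.80. Under those conditions a materially worse device would give a non-significant result more often than not, and only wide margins could be met. More lesions than the minimum, or positive correlation between paired lesions, could improve precision but would not supply the missing criterion.

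**What to change.** **Section 11.** Replace the chi-square as the basis for the efficacy conclusion with the NTAP minus standard-of-care difference in response. Estimate it separately for warts and molluscum, with a 95% CI that accounts for lesions within participant. The investigator should name the response category, image type and time point. State that a non-significant chi-square is not evidence of equality.

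**Section 1.0.** Reword the hypothesis as estimating that difference, with no equality claim. Keep an equality claim only if a justified margin is fixed before any outcome data by arm are reviewed: the lower confidence limit must clear it for non-inferiority, and both limits for equivalence. Timing matters because section 15.0 says "A cumulative data assessment will be conducted every other month throughout the" study, and the resulting report may include efficacy data.

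**Cost.** The hypothesis must be reworded and an analysis paragraph written, including a success definition and a method for clustered lesions; if a margin is wanted, it must also be justified. No extra participants or visits are needed. The downside is that most margins would not be met at this size, so the trial would report an estimate rather than show equality.

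**Separate minor point.** Section 1.0 names cryotherapy as the comparator for both diseases, while sections 3.0 and 10.0 name cantharidin for molluscum. These sections must be reconciled.

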10.0 Study Design / Methods

- A chart review of patient the patient's medical record will be completed and the following information will be collected for research purposes: DOB, demographics, contact information and diagnosis.
- Skin irritants, emollients, topical medications and other topical products cannot be applied to the study area 4 weeks prior to the start of the study and throughout the duration of the study. Details of what can and cannot be used can be discussed any time.
- During a clinical care visit, if a patient is eligible and agrees to participate, lesions will be selected by the dermatologist prior to procedure. The lesions will be marked randomly for a certain treatment regimen and photographs will be taken before each treatment and after completion of the study. Identifiers will be covered to protect identity. All images will be saved on a MUSC network secure box drive using a subject study number.
- The number of lesions treated will not exceed SOC recommendations. They will be determined by provider assessment and anatomical location.
- Participants with one lesion will receive either NTAP or standard of care (SOC). SOC is

Page 8 of 13

cryotherapy for warts and cantharidin for molluscum. Participants with greater than 2 lesions will receive equal treatment of NTAP and SOC. The number of lesions treated will be based off the providers assessment and anatomical location. Treatment of a single lesion or an odd number of multiple lesions will be based off a randomized list.

- All SOC lesions will be treated first to reduce the number of patients not wanting return to the more painful modality.
- All people in the room will be provided eye shields that must be worn during treatment. The patient will be placed in a comfortable position before the lesion is cleaned with alcohol.
- Each lesion will be treated for 1-2 minutes. Total treatment duration will be no longer than 20 minutes.
- The interval between treatment groups will about 1 minute.
- There will be a follow-up phone call a week after treatment to check on resolution and report any adverse events. If an adverse event is reported the study team members will access if the patient needs to be seen by a provider that day.

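### The hypothesis names cryotherapy as the comparator for both diseases, but molluscum controls receive cantharidin, and the plan does not say how the two diseases are to be analysed together or apart

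*Combined protocol and SAP*

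**What the plan says.** Section 1.0 (Objectives / Specific Aims) gives the trial's only hypothesis: "NTAP will be an equally efficient and painless alternative to cryotherapy for the treatment of molluscum and warts". The phrase "alternative to cryotherapy for the treatment of molluscum and warts" names one comparator for two diseases, and the sentence covers both efficacy and pain.

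Section 3.0 (Intervention to be studied) sets the control by disease, with "standard of care being cryotherapy for warts and cantharidin for molluscum". Section 10.0 (Study Design / Methods) repeats the same split. Section 3.0 also sets a recruitment target for each disease, "The study will continue until at least 68 warts and 68 molluscum are treated", and the allocation, "Half the lesions will be treated with plasma and the other half with standard of care".

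Section 6.0 (Number of Subjects) gives one figure, "Total of 150 would be required (half control, half NTP", with one set of response probabilities and no division by disease or by control treatment. Section 11 (Data Management) gives one line on the comparison, "Chi-square analysis comparing the proportions of successes", and does not mention disease.

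**The concern.** The hypothesis and the allocation do not describe the same trial. A reader who takes section 1.0 at its word expects a comparison with cryotherapy in molluscum, and no molluscum lesion is assigned to cryotherapy. The pain half of the hypothesis has the same gap, because the visual analogue scores of molluscum controls will describe cantharidin.

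The analysis text does not close the gap. With one total, one set of rates and one unqualified test line, the choice between pooling, stratifying and separating the diseases is left open and could be made after the results are known. That matters more than usual here because the claim is one of equality: averaging two unlike differences moves the result towards the conclusion the trial hopes to reach. A small overall difference could then be reported as equality with cryotherapy in both diseases, when it measures that in neither. A common effect across the diseases cannot be presumed either, since section 2.0 says that efficacy in molluscum is untested.

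**Working it through.** **1. Comparator named against comparator assigned.**

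| Disease | Comparator in section 1.0 | Control in sections 3.0 and 10.0 | Minimum lesions (section 3.0) |
|---|---|---|---|
| Warts | Cryotherapy | Cryotherapy | 68 |
| Molluscum | Cryotherapy | Cantharidin | 68 |

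The minimum total is 68 + 68 = 136. The share with no cryotherapy comparator is 68/136 = 50%. With half the lesions on each treatment, each disease has 68/2 = 34 against 34.

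**2. What the sizing and analysis text settles.** The total of 150 in section 6.0 rests on probabilities of 1/3 each under the null and 9/17, 3/17 and 5/17 under the alternative. None of these is labelled as a cryotherapy rate, a cantharidin rate or a molluscum rate, so the calculation does not show which comparison it serves. Whether 150 follows from those inputs is a separate matter and is not needed here.

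**3. What a pooled difference would estimate.** Let d_W be the NTAP-minus-cryotherapy difference in warts and d_M the NTAP-minus-cantharidin difference in molluscum. With equal numbers per disease and treatment, the pooled difference is (d_W + d_M)/2. It equals either component only if the two are equal.

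An illustration with assumed rates (the documents give none for either control):

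- Warts: 53% on NTAP, 40% on control, d_W = +13 points.
- Molluscum: 40% on NTAP, 53% on control, d_M = −13 points.
- Pooled NTAP: (53 + 40)/2 = 46.5%. Pooled control: (40 + 53)/2 = 46.5%. Pooled difference: 0.
- Treatment-by-disease difference: 13 − (−13) = 26 points.

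An equally weighted stratified estimate is also (13 − 13)/2 = 0. Stratification alone therefore does not reveal the reversal; the separate differences and their contrast do.

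**4. Precision per disease.** The 95% half-width for a difference in proportions, with n lesions per treatment, response p in both and independent lesions, is 1.96 × √(2p(1 − p)/n).

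- One disease, n = 34, p = 0.5: 1.96 × √(0.5/34) = 0.238, about 24 points. At p = 9/17 it is 0.237.
- Both diseases combined, n = 68, p = 0.5: 1.96 × √(0.5/68) = 0.168, about 17 points.
- If the 150 in section 6.0 counts lesions and divides equally between diseases (both assumptions), n = 37.5 and the half-width is 1.96 × √(0.5/37.5) = 0.226, about 23 points.

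**5. The illustration at this size.** For 53% against 40% with 34 each, the standard error is √(0.53 × 0.47/34 + 0.40 × 0.60/34) = 0.120. The interval is 13 ± 23.5 points, or −10.5 to +36.5. For the 26-point contrast between diseases, the half-width is √2 × 23.5 = 33 points. Neither interval excludes zero.

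**The case against.** The strongest reply is that the hypothesis sentence is loose drafting. The control for each disease is stated twice and consistently, so cryotherapy in section 1.0 may simply stand for standard of care. Giving each disease its own standard of care is a legitimate design, and the broader objective in section 1.0 (safety and efficacy in both diseases) does not depend on cryotherapy. This explains how the mismatch may have arisen. It does not remove it, because the sentence is the only statement of what the trial intends to claim.

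Two stronger readings are tempting, and the documents support neither:

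- **That the plan specifies one pooled test.** The single total and single chi-square line make pooling plausible, but no section states it. The separate 68 and 68 targets and the disease-specific dermoscopic criteria in the Study Endpoints section fit separate analyses at least as well. What can be said is that the plan is silent.
- **That the molluscum half of the trial cannot be answered.** Only the comparison with cryotherapy is out of reach. NTAP against cantharidin is randomised and concurrent within the trial, and can be estimated.

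It is also fair to say that the reversal in the illustration is chosen to cancel exactly. Nothing in the documents suggests opposite effects, and at 34 against 34 lesions a 13-point difference would not stand out in either disease alone. The example shows what pooling could hide, not what is expected to happen.

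**Conclusion.** The point holds as a contradiction between section 1.0 and sections 3.0 and 10.0, together with a gap in sections 6.0 and 11. The contradiction is textual and rests on no assumption: as worded, the hypothesis has no comparator data for molluscum, which is 50% of the minimum lesion target. The gap is that the plan does not say how the diseases are combined or kept apart. The harm from pooling is conditional on pooling being done and on the two differences being unlike.

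The precision figures assume the minimum targets, exact halving, response near 50% and independent lesions. Section 3.0 allows up to 20 lesions per patient, and correlation within patients could move the width either way. The trial can still give interpretable results in both diseases if the claim and the analysis are matched to the assigned controls. No view is taken on which control is clinically right.

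**What to change.** 1. Reconcile section 1.0 with sections 3.0 and 10.0. State one hypothesis per disease, for efficacy and for pain, against the control that disease is actually assigned. As sections 3.0 and 10.0 now read, that is cryotherapy for warts and cantharidin for molluscum.
2. In section 11, state before any outcome data are examined that each disease's NTAP-minus-control difference will be reported with its confidence interval.
3. If a combined test is wanted, stratify it by disease and show the treatment-by-disease difference beside it. Do not describe the combined result as a comparison with cryotherapy.
4. In section 6.0, say which comparison the total serves and how it divides between the diseases.

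The cost is a wording change and one stratified analysis; no treatment or visit changes. The drawback is that limited precision becomes visible: about ±24 points per disease against about ±17 for the combined figure, and the contrast between diseases is less precise still (about ±33 points in the illustration).
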